9.2 Subject Disposition

The number and percent of subjects in each analysis set (Full Analysis Set, Safety Analysis Set, and PK Analysis Set), who complete or discontinue treatment (including reasons for discontinuing), and who complete or discontinue from the study (including reasons for discontinuing) will be summarized using the Full Analysis Set.

9.3 Important Protocol Deviations

Protocol deviations will be recorded during the conduct of the study and those identified as important will be listed by subject using the Full Analysis Set.

9.4 Demographic and Baseline Characteristics

Descriptive summaries of subject demographics and baseline characteristics will be produced using the Safety Analysis Set. Demographic data will include:

- Race: American Indian or Alaska Native, Asian, Black or African American, Native Hawaiian or Pacific Islander, White, and Other. If one subject has more than once race is reported, the subject will be categorized as More than One Race Reported.
- Ethnicity: Not Hispanic or Latino, Hispanic or Latino, Not Reported, Unknown, and Other.

- Sex: Male and Female
- Age at screening in years
- Baseline weight
- Baseline height
- Baseline BMI

Additionally, demographic and baseline characteristic data for patients with NASH or suspected NASH cohorts will include:

- HSD17B13 Genotype (T/T vs T/TA)
- PNPLA3 Genotype (C/C vs G/G)

9.5 Medical History

Medical History will include previously diagnosed medical conditions, medication use over the previous 30 days, including vitamins, over-the-counter medications, prescription drugs, recreational drugs or supplements and alcohol and tobacco use. Medical history will be summarized both by number and proportion of participants receiving therapies of interest presented by system organ class (SOC) and preferred term (PT) as coded by the Medical Dictionary for Regulatory Activities (MedDRA) version 23.0 or later.

9.6 Safety Analyses

All safety summaries outlined in this section will be created using the Safety Analysis Set.

9.6.1 Adverse Events

Adverse event (AEs) will be coded using the Medical Dictionary for Regulatory Activities (MedDRA, the latest available version) and data will be summarized by System Organ Class (SOC) and a Preferred Term.

A table providing an overall summary of AEs will be produced which will include the number of TEAEs; the number and percentage of participants reporting at least one: TEAE, TESAE, grade 3 (severe) or higher TEAE, TEAE related to study treatment (possibly or probably related to ARO-HSD), TESAE related to study treatment, grade 3 or higher TEAE related to the investigational product and TEAE leading to drug or study withdrawal.

Descriptive statistics summaries of subject incidence will be summarized for all TEAEs, treatment-related TEAEs, TESAEs, treatment-related TESAEs, and TEAEs resulting in investigational product withdrawal or study discontinuation, treatment emergent fatal AEs, TEAE at injection site and TEAE related to LISR will be tabulated by SOC in alphabetical order and PT in descending order of frequency. Descriptive summaries will include count and percent of subjects as well as number of events..

Descriptive statistics summaries of subject incidence of TEAEs, TEAE at injection site and TEAE related to LISR by SOC, PT, and severity will be provided. Subjects will be counted once under the highest severity reported within each SOC and PT. The events will be counted the number of times they occur within each SOC and PT.

Descriptive statistics summaries of subject incidence of TEAEs by SOC, PT, and relationship to investigational product will be provided. Subjects will be counted once under the closest relationship reported within each SOC and PT. Events will be counted the number of times they occur within each SOC and PT.

A by-subject AE data listing, including verbatim term, MedDRA SOC and PT, TEAE flag, seriousness, severity, outcome and relationship to study treatment will be provided. Separate listings will be generated for SAEs.

9.6.2 Laboratory Test Results

Laboratory assessments include biochemistry, coagulation, hematology, urinalysis. Clinical laboratory values will be expressed using the International System of Units (SI).

Descriptive statistics summaries of quantitative laboratory tests will be provided by scheduled visit. Derived changes and percent changes from baseline to each scheduled postdose visit will be included.

Tables of shifts from baseline to the worst post-baseline grade (graded according to the NCI Common Toxicity Grading Criteria in Appendix A) will be provided for the following laboratory parameters: ALT, AST, GGT, ALP, total bilirubin, and CK. Unscheduled assessments will be included in the shift tables.

An eDISH plot will be created between peak Total Bilirubin vs. peak ALT, both in multiples of ULN, with horizontal and vertical lines indicating Hy's law thresholds: ALT = $3 \times$ ULN and total bilirubin = $2 \times$ ULN. For Cohorts 1-4, a single plot will be produced, with individual subjects noted as receiving either active treatment or PBO (different tick marks).

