## 7.4 **Stopping Rules**

A decision to stop the trial early or discontinue drug in an individual subject, group of subjects or to halt enrollment temporarily or permanently may be indicated based on any of the following:

- 1. A serious adverse reaction (i.e. an SAE considered at least possibly related to the IMP administration) in ONE subject; or severe non-serious adverse reactions (i.e. severe non-SAEs considered as, at least, possibly related to the IMP administration) in TWO subjects in the same cohort, independent of whether or not the events occur within the same system-organ-class.
- 2. One of the following abnormal results at least possibly related to ARO-HSD:
  - In NHV cohorts:
    - o Treatment emergent AST and/or ALT > 8X ULN which must be confirmed by repeat blood draw within 48 hours of initial results, OR

- A treatment emergent AST or ALT >3X ULN (must be confirmed on repeat) with a total bilirubin >2X ULN (must be confirmed on repeat), OR
- A treatment emergent ALT or AST >3X ULN (must be confirmed on repeat) with symptoms of RUQ pain, fever, rash or eosinophilia, OR
- A treatment emergent AST or ALT >3X ULN (must be confirmed on repeat) with an INR > 1.5 (must be confirmed on repeat) and which must not be explained by another plausible cause
- See Appendix 16.1 for treatment modification guidelines in patients with baseline/pre-dose elevated ALT or AST.

If such serious adverse reactions or severe non-serious adverse reactions occur as outlined above, enrollment and dosing in healthy volunteers will be paused pending a review of safety data and a decision on how to proceed by the DSC.

The Sponsor or PI can discontinue any patient at any time with or without DSC consultation. If such events (as described above) occur and the patient is not discontinued from the study, the reason for not discontinuing the patient will be included in DSC meeting minutes. Including, but not limited to the events listed above, the DSC may pause the study to additional dosing or dose escalation to provide time to evaluate safety data and recommend the action to be taken, which may include, but is not limited to, one of the following:

- 1. Discontinuation of a patient or group of patients from the study.
- 2. The study is stopped immediately with no further dosing
- 3. The study will continue until the current cohort is completed.

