12. APPENDIX

12.1 Appendix A: Grading Laboratory Values according to CTCAE Version 5

	Grade 1	Grade 2	Grade 3	Grade 4
Serum Chemistry				
Alanine aminotransferase, increased	Normal baseline: > ULN – 3.0 x ULN Abnormal baseline: 1.5 x – 3.0 x baseline	Normal baseline: > 3.0 x – 5.0 x ULN Abnormal baseline: > 3.0 x – 5.0 x baseline	Normal baseline: > 5.0 x – 20.0 x ULN Abnormal baseline: > 5.0 x – 20.0 x baseline	Normal baseline: > 20.0 x ULN Abnormal baseline: > 20.0 x baseline
Alkaline Phosphatase, increased	Normal baseline: > ULN – 2.5 x ULN Abnormal baseline: 2.0 x – 2.5 x baseline	Normal baseline: > 2.5 x – 5.0 x ULN Abnormal baseline: > 2.5 x – 5.0 x baseline	Normal baseline: > 5.0 x – 20.0 x ULN Abnormal baseline: > 5.0 x – 20.0 x baseline	Normal baseline: > 20.0 x ULN Abnormal baseline: > 20.0 x baseline
Aspartate aminotransferase, increased	Normal baseline: > ULN – 3.0 x ULN Abnormal baseline: 1.5 x – 3.0 x baseline	Normal baseline: > 3.0 x – 5.0 x ULN Abnormal baseline: > 3.0 x – 5.0 x baseline	Normal baseline: > 5.0 x – 20.0 x ULN Abnormal baseline: > 5.0 x – 20.0 x baseline	Normal baseline: > 20.0 x ULN Abnormal baseline: > 20.0 x baseline
Creatine phosphokinase, increased	> ULN – 2.5 x ULN	> 2.5 – 5.0 x ULN	> 5 – 10 x ULN	> 10 x ULN
Gamma glutamyl transferase, increased	Normal baseline: > ULN – 2.5 x ULN Abnormal baseline: 2.0 x – 2.5 x baseline	Normal baseline: > 2.5 x – 5.0 x ULN Abnormal baseline: > 2.5 x – 5.0 x baseline	Normal baseline: > 5.0 x – 20.0 x ULN Abnormal baseline: > 5.0 x – 20.0 x baseline	Normal baseline: > 20.0 x ULN Abnormal baseline: > 20.0 x baseline
Total bilirubin, increased	Normal baseline: > ULN – 1.5 x ULN Abnormal baseline: > 1.0 x – 1.5 x baseline	Normal baseline: > 1.5 x – 3.0 x ULN Abnormal baseline: > 1.5 x – 3.0 x baseline	Normal baseline: > 3.0 x – 10.0 x ULN Abnormal baseline: > 3.0 x – 10.0 x baseline	Normal baseline: > 10.0 x ULN Abnormal baseline: > 10.0 x baseline

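### The SAP's only joint aminotransferase-bilirubin display uses ALT alone, while the protocol's combined liver criterion for Cohorts 1-4 is met by AST or ALT

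*SAP*

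**What the plan says.** Protocol 7.4 lists results that may lead to stopping in the healthy-volunteer cohorts. One of them is "A treatment emergent AST or ALT >3X ULN (must be confirmed on repeat) with a total bilirubin >2X ULN", with the bilirubin value also to be confirmed on repeat. The list opens with a relatedness condition: "One of the following abnormal results at least possibly related to ARO-HSD". The synopsis, under Treatment Stopping Rules, gives the same criterion.

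SAP 9.6.2 plans one joint display: "An eDISH plot will be created between peak Total Bilirubin vs. peak ALT, both in multiples of ULN". Its Hy's law lines are at 3x ULN for ALT and 2x ULN for total bilirubin. For the volunteers, "For Cohorts 1-4, a single plot will be produced", with active and placebo subjects marked differently. AST is on neither axis.

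Elsewhere in SAP 9.6.2, quantitative laboratory tests are summarised by visit, and grade shift tables are planned for "ALT, AST, GGT, ALP, total bilirubin, and CK". The shift tables include unscheduled assessments. The SAP does not say whether the eDISH plot does.

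**The concern.** The plot uses the protocol's two thresholds but covers only one of the two enzymes that can meet the aminotransferase part of the criterion. When AST alone meets it, the plotted point lies left of the ALT line, outside the quadrant a reader checks for a combined liver signal.

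This matters because safety is the study objective, protocol 5.7 names hepatic risk, and that section cites stopping rules on both ALT and AST as mitigation. SAP section 1 says its analyses form the basis of the results in the study report. An empty quadrant in that report could be read as showing that no volunteer reached the combined criterion, and the plot cannot support that statement for AST-driven cases.

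**Working it through.** The plan gives no figure to reproduce. The check compares the two definitions. ALT, AST and total bilirubin (TBL) are in multiples of ULN.

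**Definitions**
- Protocol 7.4, numeric part: (ALT > 3 or AST > 3) and TBL > 2.
- SAP 9.6.2 quadrant: ALT > 3 and TBL > 2.

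**Illustrative cases** (values chosen for the check; the documents contain no data)

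| ALT | AST | TBL | Meets protocol thresholds | In SAP quadrant |
|---|---|---|---|---|
| 2 | 4 | 2.5 | yes | no |
| 2.9 | 3.1 | 2.1 | yes | no |
| 4 | 2 | 2.5 | yes | yes |
| 4 | 4 | 2.5 | yes | yes |
| 2 | 4 | 1.8 | no | no |

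**Where the definitions disagree.** Both were evaluated on a grid from 0.25 to 10 in steps of 0.25 (40 values per test). They disagree exactly where ALT <= 3 (12 values), AST > 3 (28 values) and TBL > 2 (32 values): 12 x 28 x 32 = 10,752 grid points. This count describes the shape of the gap and is not a probability. If a subject also counts as flagged when AST > 3 with TBL > 2, no grid point disagrees with the protocol's numeric thresholds.

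**Whether another SAP output recovers the case**
- Shift tables: with normal baselines, AST at 4x is grade 2 in SAP Appendix A. Bilirubin grade 2 is "Normal baseline: > 1.5 x – 3.0 x ULN", so 2.5x (above the protocol threshold) and 1.8x (below it) share a grade. Each parameter also has its own table, so the two results are not linked within a subject.
- By-visit summaries are group statistics and cannot show a within-subject combination.
- SAP 9.6.2 describes no by-subject laboratory listing. Protocol 12.3 mentions listings that place values relative to the normal limits, which would not mark 3x or 2x ULN.
- Adverse event tables would include the case only if the investigator judged the abnormality clinically significant or it had clinical sequelae (protocol 11.2).

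**The case against.** The strongest reply is that the documents do not contradict each other. The stopping rule operates during the study, through the DSC, the investigator and the sponsor. The plot is a descriptive figure at the end, and the SAP never says that it implements the rule. It also ignores confirmation on repeat, relatedness and timing, since the two peaks may fall on different days. Appendix 16.1 of the protocol, for subjects with baseline liver disease, triggers on ALT in every row, so an ALT axis has a precedent. The subject is not lost: a volunteer with bilirubin at 2.5x ULN appears above the bilirubin line, AST is shown in other tables, and adverse event reporting may capture the case. AST can also rise from muscle, so a single axis of the larger enzyme could mix non-hepatic rises into a liver display.

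Most of this stands and limits the weight of the point. What remains is narrow: no output described in the SAP shows a volunteer's AST together with that volunteer's bilirubin. Appendix 16.1 does not settle the matter for Cohorts 1-4, whose own criterion in 7.4 names both enzymes and who enter with normal ALT and AST.

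Three stronger readings are tempting, and the documents do not support them:
- That a stopping event could go unnoticed. The rule does not depend on this plot.
- That the signal vanishes from the report. The point is plotted in another region, and its components appear in other tables.
- That the gap has a size such as 1 of 16 active volunteers (6.3%) or 1 of 4 in a cohort (25%). Those are one hypothetical subject over the planned denominators; nothing in the documents says how likely such a subject is.

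**Conclusion.** The point holds as a minor gap in final reporting. For Cohorts 1-4, the only joint aminotransferase-bilirubin display in the SAP cannot place an AST-driven case in the Hy's law quadrant, although that case meets the numeric part of the protocol's combined criterion. It affects exactly the cases with AST above 3x, ALT at or below 3x and bilirubin above 2x ULN. No frequency can be given, and no estimate, test or decision rule in the SAP depends on the plot.

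The conclusion rests on the SAP text. The table, figure and listing formats are in a companion document that was not available. If that document already contains a by-subject listing that applies both thresholds to both enzymes, the gap is closed and only the SAP wording needs to say so.

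**What to change.** In SAP 9.6.2:

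1. Keep the planned ALT panel and add a second panel of peak total bilirubin against peak AST, both in multiples of ULN, with the same 3x and 2x lines. Separate panels are better than one axis of the larger value because they show which enzyme drove the point.
2. Add a listing of any subject with AST or ALT above 3x ULN and total bilirubin above 2x ULN. Show the dates of the values and CK, so that peaks on different days and AST rises of muscle origin can be recognised.
3. State that scheduled and unscheduled results count for both outputs. The protocol criterion depends on repeat draws, and the SAP now includes unscheduled results explicitly only for the shift tables.

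ALT, AST, total bilirubin and CK are all in the biochemistry panel of protocol 10.3.5, so no new data are needed. The cost is minor programming, one panel and a short listing. The drawback is that some non-hepatic AST rises may be displayed; the CK and date columns are there to identify them. The stopping rule itself is unaffected.

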9.6.3 Analyses of Lipid Parameter

Descriptive statistics summaries will be provided for following parameters: triglycerides, HDL-C, LDL-C, total cholesterol, non-HDL-C, and VLDL-C. Derived changes and percent changes from baseline to each scheduled postdose visit will be included.

9.6.4 Vital Signs

Descriptive statistics summaries of vital sign parameters (systolic blood pressure, diastolic blood pressure, pulse rate, body temperature and respiratory rate) will be provided by scheduled visit. Derived changes and percent changes from baseline to each scheduled postdose visit will be included.

All vital sign parameters will be listed per cohort for active drug participants, for placebo participants pooled across cohorts, as well as for all participants (active drug and placebo) considered collectively, for all time points assessed.

9.6.5 Physical Examinations

Descriptive statistics summaries of physical examination will be provided by scheduled visit, body system and abnormality.

By-participant data listings will be generated for all the physical examination data, including the Investigator assessment of clinical significance for abnormal findings, for all time points assessed.

9.6.6 *Electrocardiogram*

Descriptive statistics summaries of electrocardiogram (ECG) parameters (heart rate, PR interval, QRS interval, QT interval, and QTcF interval) will be provided by scheduled visit. Derived changes and percent changes from baseline to each scheduled postdose visit will be included. If more than one measure was collected at a scheduled visit (maximum 3), then the average value will be used.

The overall interpretation of 12-lead ECG results will be classified using frequency counts and percentages for the categories of Normal, Abnormal NCS and Abnormal CS for each treatment group for all time points assessed.

Tables of shifts from baseline to the worst post-baseline clinical significance will be provided for the overall interpretation of 12-lead ECG assessments. Additionally, subjects will be categorized and summarized per their maximum post-baseline absolute QTcF interval using limits of 450ms, 480 msec and 500 msec. They will also be categorized per their maximum change from baseline QTcB and QTcF interval using limits of 30 msec and 60 msec.

All ECG data will be presented in the by-subject data listings.

9.6.7 *Anti-drug Antibodies*

Descriptive statistics summaries (number and percent of subject with positive ADA) of anti-drug antibodies (ADA) will be provided by scheduled visit for each treatment group, pooled placebo and pooled treatment, as data applicable. Also, the titer values will be summarized descriptively for each time point by treatment if data available.

If ADA positive were observed at baseline, the postdose titer values will be compared with baseline and plotted vs time point to see if a treatment-boosted ADA happening to the subject.

If any ADA positive observed, spaghetti plots of individual plasma concentrations versus actual time will be presented by ADA category for each treatment group for PK analysis set.

All ADA data will be listed by subject for safety analysis set which has at least one ADA data reported.

9.6.8 *Exposure to Investigational Product*

The number of subjects receiving study treatment will be summarized by the total number of injections received and the duration of study. Duration of study will be calculated in weeks as: (EOS date – date of first dose + 1)/7.

9.6.9 *Exposure to Concomitant Medication*

Medications with an end date on or after the first dose of investigational product will be identified as concomitant medications. Medications will be coded using World Health Organization Drug Dictionary (WHO-DD, the latest available version). and will be reported by Anatomical Therapeutic Chemical (ATC) classification level 4 and Preferred Drug Name.

Participants who take the same medication more than once will be counted only once for that preferred term.

Descriptive statistics summaries of the number and percent of subjects who receive each concomitant medication will be summarized.

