#### **Cohort Summary**

Cohort	Population	Blinding	# Subjects	Dosing Schedule
1	NHVs	Double blind	8 (4 active:	25 mg Day 1 only
			4 placebo)	
1b	Patients with suspected NASH	Open Label	up to 6	25 mg Days 1, 29
	(biopsies on screen and day 71)		(all active)	
2	NHVs	Double blind	8 (4 active:	50 mg Day 1 only
			4 placebo)	
3	NHVs	Double blind	8 (4 active:	≤ 100 mg Day 1 only
			4 placebo)	
4	NHVs	Double blind	8 (4 active:	$\leq$ 200 mg Day 1 only
			4 placebo)	
3b	Patients with suspected NASH	Open Label	up to 6	≤100 mg Days 1, 29
	(biopsies on screen and day 71)		(all active)	
4b	Patients with suspected NASH	Open Label	up to 6	≤200 mg Days 1, 29
	(biopsies on screen and day 71)		(all active)	

Approximately 50 subjects may be enrolled in the study (not including replacements or optional expansion cohort).

**Number of Doses per Treatment:** Single dose (Cohorts 1, 2, 3, 4) or two doses (Cohorts 1b, 3b and 4b) dosed 28 days apart

**Study Duration:** For subjects in Cohorts 1 through 4, the duration of the study clinic visits is approximately 158 days from screening to the End-of-Study visit. For subjects in Cohorts 1b, 3b and 4b, the duration of the study clinic visits is approximately up to 173 days from screening to the End-of-Study visit. Additionally, all subjects will have a 90-day post-end of study visit follow-up phone call assessing compliance with contraception.

**Study Confinement:** For all NHV cohorts (1-4), clinical facility confinement will be approximately 3 days for dose administration (Day -1 through 24-hour assessments) with discharge on Day 2. Subjects will return to the clinical facility for outpatient visits per the Schedule of Assessments. Patients in Cohorts 1b, 3b and 4b will be at the facility for approximately 4 hours (2 hours before dosing and 2 hours after dosing) on dosing days.

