# 10.3.3 Electrocardiogram

A single 12-lead ECG measurement will be obtained at time points outlined in the Schedule of Assessments after the participant is semi-supine for at least 3 minutes. On dosing days ECGs will be performed pre-dose and 1 and 2 hours post-dose and may be performed more frequently if indicated. ECGs should be performed within a window of 10 minutes, prior to other invasive procedures such as blood draws. Any abnormal ECGs will be repeated in triplicate, with each measurement approximately 1 minute apart. Only abnormal ECG readings that are considered clinically significant in the opinion of the investigator need to be repeated in triplicate. Triplicate ECGs are three tracings approximately 1 minute apart. If the originally scheduled ECG is considered clinically significant, both the first tracing and the triplicate tracings will be entered into the EDC.

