5. DEFINITIONS

Day 1:

For each subject, Day 1 is defined as the first day that protocol-specified study treatment is administered to the subject.

End of Study (EOS) Date:

For each subject, the EOS date is the study completion/early termination date recorded on the eCRF.

Study Day:

For each subject, and for a given date of interest, study day is defined as the number of days relative to Day 1:

- After first dose date: study day = date of interest – Day 1 date + 1
- Prior to first dose date: study day = date of interest – Day 1 date, so that the day prior to Day 1 is Day -1

Study End Date:

The study end date is when the last subject finishes the EOS visit.

Baseline Values:

For all variables, baseline is defined as the last non-missing value obtained prior to the first dose administration on Day 1.

For ECG, if a triplicate is taken prior to the first dose administered on Day 1, baseline is defined as the mean over the set of triplicate assessments.

Analysis Day:

Selected endpoints will be summarized based on Analysis Day defined using Study Day as below.

Scheduled Visit/ Analysis Day	Day 8	Day 15	Day 29	Day 43	Day 57	Day 71	Day 85	Day 99	Day 113
Study Day Window Cohort 1-4	[6,10]	[13,17]	[27,31]	[41, 45]	[55,59]	[69,73]	[83,87]	[97,101]	[111,115]
Study Day Window Cohort 1b,3b,4b	NA	[13,17]	[27,31]	NA	[55,59]	[66,76]	[83,87]	NA	[108,118]

If there is more than one record in a study day window, the analytical record for that specific analysis day will be defined as the record closest to the scheduled visit day. If two records are equidistant from the scheduled visit day, then the earlier record will be chosen. If there are multiple records on the same day, the last record will be used.

Duration of study:

EOS date – Day 1 date + 1

Treatment-Emergent Adverse Event (TEAE):

TEAEs are defined as adverse events occurring on or after the first dose of study treatment through EOS or pre-treatment existing conditions that worsen after the investigational product administration.

Treatment-emergent SAEs (TESAEs):

TESAEs are defined as serious adverse events occurring on or after the first dose of study treatment through EOS or pre-treatment existing conditions that worsen after the investigational product administration.

TEAE at Injection Site:

TEAE occur at the injection site. MedDRA Preferred Terms which are included in LISR are listed in Protocol Section 16.2.

TEAE Related to Local Injection Site Reaction (LISR):

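### SAP 9.6.6 averages ECGs per visit, not per time point: read literally, Day 29 mixes the pre-dose tracing with the 1 h and 2 h post-dose tracings and shrinks an acute change in the by-visit table

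*SAP*

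**What the plan says.** SAP 9.6.6 summarises heart rate, PR, QRS, QT and QTcF descriptively by scheduled visit. It adds: "Derived changes and percent changes from baseline to each scheduled postdose visit will be included". Its rule for several values is: "If more than one measure was collected at a scheduled visit (maximum 3), then the average value will be used". The same section also categorises each subject's maximum post-baseline QTcF (450, 480 and 500 msec) and maximum change in QTcB and QTcF (30 and 60 msec). It does not say whether those maxima are taken over individual tracings or over averages.

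Protocol 10.3.3 sets how ECGs are taken: "A single 12-lead ECG measurement will be obtained at time points outlined in the Schedule of Assessments". It continues: "On dosing days ECGs will be performed pre-dose and 1 and 2 hours post-dose and may be performed more frequently if indicated". A clinically significant abnormal tracing is repeated in triplicate, and then "both the first tracing and the triplicate tracings will be entered into the EDC".

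The Protocol Cohort Summary gives the dosing: "Single dose (Cohorts 1, 2, 3, 4) or two doses (Cohorts 1b, 3b and 4b) dosed 28 days apart". In Table 2 the Day 29 visit of the patient cohorts is one column with ECGs at 0, 1 and 2 h.

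SAP Section 5 defines ECG baseline as the mean of a triplicate where one was taken before the first dose. For endpoints summarised by Analysis Day, which it does not name, it also says: "If there are multiple records on the same day, the last record will be used".

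**The concern.** The averaging rule works on visits, while the protocol collects dosing-day ECGs at time points within a visit. On Day 29 the routine number of tracings in the visit is three, exactly the number the rule allows for, and one of the three precedes the dose. A programmer who follows the text would produce a Day 29 value that is one third pre-dose.

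Safety is the objective of this first-in-human study, and Protocol 12.3 plans a summary of ECG changes from baseline. In Table 2 no 24 h ECG follows the second dose, and the next scheduled ECG is at end of study. The 1 h and 2 h tracings on Day 29 are therefore the only scheduled look at an acute ECG effect after repeat dosing, and this rule would blunt it in the by-visit table.

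**Working it through.** The documents give no QTc effect size, SD or power figure, so there is no plan figure to reproduce. The check is direct arithmetic on the rule as written.

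**Inputs**
- Day 29 ECGs: three (0, 1, 2 h), Cohorts 1b, 3b and 4b (Protocol Table 2).
- 0 h is pre-dose, and each ECG is routinely a single tracing (Protocol 10.3.3).
- Patients concerned: 3 cohorts × up to 6 = up to 18, before the extra patients the protocol permits.
- Rule: visit value = (E0 + E1 + E2)/3 (SAP 9.6.6).

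**Share of the effect kept.** Let D be the peak change from the Day 1 baseline.

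| Change at pre-dose, 1 h, 2 h | Visit average | Share of peak |
|---|---|---|
| 0, D, D | 2D/3 | 67% |
| 0, D/2, D | D/2 | 50% |
| 0, 0, D or 0, D, 0 | D/3 | 33% |
| D/2, D, D | 5D/6 | 83% |
| D, D, D | D | 100% |

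A time-point table keeps 100% at the peak in every row. As an illustration only, since the documents give no value for D: for D = 10, 15 or 30 msec the averaged table shows 6.7, 10 or 20 msec in the first row, and 3.3, 5 or 10 msec in the third.

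**Does averaging earn this back in precision?** Assume independent tracings with common SD s, one baseline tracing, and the 0, D, D pattern. Signal over noise, in units of D/s:
- mean of all three: (2/3)/√(1 + 1/3) = 0.577
- 2 h tracing alone: 1/√2 = 0.707
- mean of 1 h and 2 h: 1/√(1 + 1/2) = 0.816

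The three-way mean is 18% below the 2 h tracing alone (0.577/0.707 = 0.816) and 29% below the post-dose mean (0.577/0.816 = 0.707). So it does not.

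**The cap of three.** A time point repeated in triplicate holds 1 + 3 = 4 entered tracings. Day 29 then holds 2 + 4 = 6 if one time point is repeated, and 3 × 4 = 12 if all are.

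**Section 5 against 9.6.6.** If the same-day rule applied to ECGs, Day 29 would be the 2 h tracing. For 0, D, D that gives D against 2D/3. For 0, D, 0 it gives 0 against D/3. The choice of rule changes the number.

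**Maximum-change categories, only if visit averages feed them.** For 0, D, D the peak change must exceed 30/(2/3) = 45 msec or 60/(2/3) = 90 msec to cross the 30 or 60 msec limit. For 0, 0, D it must exceed 90 or 180 msec.

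**Day 1.** Tables 1 and 2 schedule pre-dose, 1 h and 2 h ECGs on Day 1 in all cohorts. If Day 1 were treated as one visit, the pre-dose tracing, normally the baseline itself, would be averaged into its own post-dose value and the same fractions would apply.

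**The case against.** The strongest reply is that the rule was meant for triplicates. Three is the size of the only replicate scheme in the protocol, and the baseline rule in SAP Section 5 averages a triplicate, so 9.6.6 may be its post-baseline counterpart. The SAP also uses visit loosely: vital signs are summarised by scheduled visit although several are taken on Day 1, and 9.6.6 itself reports ECG interpretation for every time point. The table layouts sit in a companion document not available here. Averaging a Day 1 baseline into its own post-dose value would be odd enough to suggest that nobody intended it.

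This stands as an account of likely intent. It does not repair the text. The Analysis Day table in Section 5 treats Day 29 as one scheduled visit. Where the SAP means a triplicate it says so, and 9.6.6 does not. The triplicate reading still leaves the fourth entered tracing unhandled.

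Three stronger inferences are tempting, and the documents do not support them:
- That every QTc effect is diluted. An effect sustained from Day 1 is fully kept.
- That the two SAP rules contradict each other. The same-day rule covers unnamed endpoints, and a specific ECG rule would normally prevail, so what is missing is a statement of precedence.
- That the outlier categories are blunted. They use subject maxima, and nothing says that averages feed them.

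It is also true that ECG output is descriptive, no hypothesis is tested, the primary endpoint is related adverse events, and all ECG data are listed by subject.

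**Conclusion.** The point holds as a defect of wording with a real consequence in one planned safety table. Followed literally, 9.6.6 mixes pre-dose and post-dose ECGs on Day 29 in Cohorts 1b, 3b and 4b. The by-visit mean then keeps one third to two thirds of the peak for an acute change that is absent pre-dose and present at 1 h, 2 h or both. That range rests on the literal reading and on a wholly acute effect. The loss is 17% if half the effect is already present pre-dose, and nil if it is sustained.

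Day 29 blending does not touch the healthy-volunteer cohorts, which receive one dose on Day 1. They are affected only if Day 1 is handled as one visit. The handling of four tracings, the precedence over Section 5 and the input to the maximum categories are gaps in specification rather than shown errors. The point deserves correction before database lock, but it does not threaten the primary endpoint.

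**What to change.** Amend SAP 9.6.6 as follows:

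- Summarise ECG values and changes from baseline by nominal time point (pre-dose, 1 h, 2 h, 24 h and so on), with Day 29 pre-dose, 1 h and 2 h as separate rows.
- Average only replicate tracings within the same nominal time point. State whether the first tracing is included with the triplicate, and treat it the same way at baseline and after it, so that a change score does not compare differently built means. Either choice is workable if it is consistent with Section 5.
- State that 9.6.6 overrides the same-day rule in Section 5 for ECGs.
- State that the maximum QTcF and maximum-change categories use time-point values, not averages across time points in a visit.

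The cost is a short SAP edit and a few more table rows. No new data or protocol change is needed.
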